**Physiological effects**

At low concentrations such as those that will be used in this study, Xenon has effects similar to nitrous oxide (laughing gas). Nine out of 10 patients experience light headedness, paraesthesia, euphoria or a mild 'drunk' feeling, which is short lived and resolves within 2-3 minutes of breathing the gas (73-75).

**Safety considerations**

**Hyperpolarized Xenon gas MR Imaging in Radiotherapy**

At high concentrations xenon has anaesthetic properties. The minimum alveolar concentration (MAC) of xenon at sea level is 70% (77). Our patients will breathe a fraction of inhaled xenon (FiXe) considerably lower than this, and will inhale a single breath and therefore not approach the gas equilibrium that is required when defining MAC. Our patients will inhale 1L from residual volume, resulting in an approximate fraction of xenon (FXe) of 10-30%. The alveolar FXe would tend to be marginally lowered due to Xe in the anatomical deadspace of the large airways, and marginally raised due to Xe not entering non- or slowly communicating air spaces within the lungs. Thus the FXe that our patients will be exposed to is considerably below the dose required to induce anaesthesia, and well within safe limits. It is not possible for patients to breathe more than 1 L of xenon, since they are given a single bag of the gas. This procedure may be repeated up to four times during one imaging session. In the event that breathing and scanning are not entirely synchronised, one or two xenon breath holds may need to be repeated; so in total, each participant will undergo a maximum of 24 hyperpolarized Xe-129 breath holds during the four imaging visits over the 9-month study period.

A further safety consideration is patients' oxygenation, since they will be inhaling 1 L of anoxic gas, followed by a breath hold. However, participants will only be exposed to this low oxygen fraction for a single breath hold. The breath hold is approximately 30 seconds, although patients are free to take another breath sooner if they cannot manage this long. The amount of oxygen available in 3.5 L of 11% oxygen is 385 mL, which is considerably more than the oxygen requirement for the duration of the breath hold (assuming oxygen use is 250 mL/ min). These calculations assume all gas within the lungs is in communication with inhaled gas, which is often not the case in respiratory disease, however the safety margins are extremely large. Reassuringly, studies in chronic obstructive pulmonary disease (COPD) patients using this breathing technique observed a mean fall in oxygen saturations of only 1.2 % of baseline during observation at 2 minute intervals for 10 minutes (72). In the unlikely event that a patient desaturates by more than 10% immediately following Xe inhalation, this manoeuvre will not be repeated.

Our patients will be carefully observed and monitored throughout the study, including direct visual observation, heart rate, respiratory rate and arterial oxygen saturations. The minimum number of people in attendance during a scan is two. This includes a doctor or allied health care professional such as a nurse or radiographer, who is solely responsible for patient monitoring, safety and well-being. They will be aware of potential risks of Xe, and appropriately trained in how to respond to any adverse sequelae arising. It also includes a technician/ radiologist who is responsible for acquiring images. In the event of any untoward medical event occurring mid-scan, staff can reach the patient immediately. As in all clinical areas throughout the Oxford Hospital Trust, emergency drugs and equipment are readily available and staff are trained in their use. This includes supplementary oxygen and resuscitation equipment.

All participants will be monitored for at least 30 minutes after the final hyperpolarized xenon dose before they are discharged home. It is likely approximately 3 hours will have elapsed since administration of the first hyperpolarized xenon dose by this time. Participants will receive a telephone consultation 24 hours after completion of hyperpolarized Xe-129 MRI to review any

**Hyperpolarized Xenon gas MR Imaging in Radiotherapy**

AEs that have occurred in the interim following discharge. Furthermore, participants will attend hospital and see the Oncology clinical team on a daily basis during radiotherapy when they will have the opportunity to report any AEs relating to hyperpolarized Xe-129 gas. The study schedule includes follow-up by both the study team and Oncology clinical team in out-patient clinic at regular intervals throughout the 9-month trial duration. This will allow for review of possible AE/SAE two weeks after each hyperpolarized xenon scanning session.

Following the final xenon administration at the 3-month post-radiotherapy follow-up visit, participants will also receive a telephone consultation two weeks later to review AE/SAEs.

A 'Physician information sheet' documenting possible effects of Xe and appropriate medical responses has been drawn up, and will be provided to all those involved in Xe imaging.

**10.2. Production, Storage and Dispensing of IMP**

Xe-129 will be isolated from a gas mixture of 1.0% xenon, 10% nitrogen and 89% helium, manufactured in the USA and supplied by Spectra Gases Ltd, Littleport Cambridgeshire. It will be polarised via spin exchange optical pumping by laser, using the Polarean 9800 hyperpolarisation system. Xe-129 will then be frozen to isolate it from other gases and sublimated into Tedlar plastic bags for administration to participants via inhalation. The gas is labelled in accordance with EU trial directive requirements.

Each batch of Xe-129 will be tested using a Polarean 2881 polarization measurement system to ensure sufficient xenon gas is hyperpolarized to enable lung imaging. All staff involved in the process of Xe-129 manufacture will be trained to ensure that the manufacture is conducted safely to the correct technical specification. The manufacturing facility is licensed by the MHRA and each batch is manufactured to GMP standard and certified for release to the investigator by a Qualified Person according to the approved Standard Operating Procedures.

***Calibration***

Calibration involves the patient breathing a small volume of xenon of approximately 100mL mixed with medical grade nitrogen for a total volume of 1L. The patient will be instructed to perform a standard breath hold for a short period of time (approximately 2 seconds). This is a set-up procedure for the scan enabling optimization of Xe-129 MR parameters according to patient height and weight as well as a practice run for the patient. The output from calibration (flip angle measurement) enables the best quality Xe-129 MR images to be acquired for each individual and is not be used to evaluate the study endpoints.

For calibration, hyperpolarization will take up to 10 minutes. The same manufacturing process as clearly described by SOPs to produce up to 1L of hyperpolarized Xe-129 will be adhered to. The only difference is the length of hyperpolarization time resulting in a much smaller volume (100mL) of hyperpolarized xenon gas being produced. Xe-129 will be isolated from other gases and

**Hyperpolarized Xenon gas MR Imaging in Radiotherapy**

sublimated into Tedlar plastic bags in Radiology for administration to participants via inhalation in the MR suite. To make a total volume of 1L, medical grade nitrogen is added. These small calibration doses are not considered to be IMPs and do not require QP release.

**10.3. Compliance with Trial Treatment**

Compliance auditing is not relevant to use of hyperpolarized xenon: a dose is only given by radiographers/ radiologists during the MR regional lung imaging itself. However, the volume of Xe-129 inhaled will be recorded on the CRF.

**10.4. Accountability of the Trial Treatment**

Medical grade xenon and nitrogen will be supplied by Spectra Gases Ltd, Littleport Cambridgeshire to Oxford Thoracic Imaging Centre where the gas will be polarized. The duration of hyperpolarization will be up to 70 minutes. Hyperpolarized xenon may be kept frozen for a short time (less than 30 minutes) before thawing. After thawing, bags of hyperpolarized xenon will be labeled with the patient's ID and the expiry date and time. Hyperpolarized xenon will be used within 30 minutes of thawing.

**10.5. Concomitant Medication**

Patients' medications will be recorded at baseline and at each follow-up visit.

**10.6. Post-trial Treatment**

The proposed study is an interventional study. As such all participants will receive best standard care throughout and this will continue without interference following study completion.

**11. SAFETY REPORTING****11.1. Definitions**

|                                |   |
|--------------------------------|---|
| Adverse Event (AE)             | Any untoward medical occurrence in a participant to whom a medicinal product has been administered, including occurrences which are not necessarily caused by or related to that product.   |
| Adverse Reaction (AR)          | 
An untoward and unintended response in a participant to an investigational medicinal product which is related to any dose administered to that participant.
 
The phrase "response to an investigational medicinal product" means that a causal relationship between a trial medication and an AE is at least a reasonable possibility, i.e. the relationship cannot be ruled out.
 
All cases judged by either the reporting medically qualified professional or the Sponsor as having a reasonable suspected causal relationship to the trial medication qualify as adverse reactions.
   |
| Serious Adverse Event (SAE)    | 
A serious adverse event is any untoward medical occurrence that:
 
 
• results in death
 
• is life-threatening
 
• requires inpatient hospitalisation or prolongation of existing hospitalisation
 
• results in persistent or significant disability/incapacity
 
• consists of a congenital anomaly or birth defect.
 
 
Other 'important medical events' may also be considered serious if they jeopardise the participant or require an intervention to prevent one of the above consequences.
 
NOTE: The term "life-threatening" in the definition of "serious" refers to an event in which the participant was at risk of death at the time of the event; it does not refer to an event which hypothetically might have caused death if it were more severe.
 |
| Serious Adverse Reaction (SAR) | An adverse event that is both serious and, in the opinion of the reporting Investigator, believed with reasonable probability to be due to one of the trial treatments, based on the information provided.  |

**Hyperpolarized Xenon gas MR Imaging in Radiotherapy**

|   |  |
|---|--|
| Suspected Serious Adverse Reaction (SUSAR) | 
A serious adverse reaction, the nature and severity of which is not consistent with the information about the medicinal product in question set out:
 
 
• in the case of a product with a marketing authorisation, in the summary of product characteristics (SmPC) for that product
 
• in the case of any other investigational medicinal product, in the investigator's brochure (IB) relating to the trial in question.
 
 |
|---|--|

NB: to avoid confusion or misunderstanding of the difference between the terms “serious” and “severe”, the following note of clarification is provided: “Severe” is often used to describe intensity of a specific event, which may be of relatively minor medical significance. “Seriousness” is the regulatory definition supplied above.

Any pregnancy occurring during the clinical trial and the outcome of the pregnancy should be recorded and followed up for congenital abnormality or birth defect, at which point it would fall within the definition of “serious”.

### **11.2. Causality**

The relationship of each adverse event to the trial medication must be determined by a medically qualified individual according to the following definitions:

**Related:** The adverse event follows a reasonable temporal sequence from trial medication administration. It cannot reasonably be attributed to any other cause.

**Not Related:** The adverse event is probably produced by the participant's clinical state or by other modes of therapy administered to the participant.

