### **11.3. Procedures for Recording Adverse Events**

All AEs observed by the investigator or reported by the patient during and for 24 hours after Xe-129 lung MRI are reported on the case report forms. A member of the research team will contact the participant by telephone 24 hours after completion of hyperpolarized Xe-129 MR imaging to record any AEs that may have occurred after leaving the hospital. These will be clearly documented on the patient CRFs. Thereafter only adverse events where there is a reasonable possibility of a relationship to inhaled xenon (adverse reactions) as judged by the chief investigator, and any adverse event considered by the chief investigator to be of medical interest/importance are reported. These events will be reported on the case report forms.

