**Hyperpolarized Xenon gas MR Imaging in Radiotherapy**

The following information will be recorded: description, date of onset and end date, severity, assessment of relatedness to trial medication, other suspect drug or device and action taken. Follow-up information should be provided as necessary.

The severity of events will be assessed on the following scale: 1 = mild, 2 = moderate, 3 = severe.

AEs considered related to inhaled xenon as judged by a medically qualified investigator or the Sponsor will be followed either until resolution, or the event is considered stable.

It will be left to the investigator's clinical judgment whether or not an AE/ AR is of sufficient severity to require the patient's removal from Xe-129 MRI scanning. A patient may also voluntarily withdraw from study procedures if they tolerate it poorly. Further details of withdrawal are presented in Section 9.8.

In the event of symptoms arising, patients will be given appropriate care and medical supervision until symptoms resolve, or the condition becomes stable. Every effort will be made to gather outcome data on patients through study follow-up, or general practitioner/ hospital staff unless the patient is specifically withdrawn consent to such efforts.

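### Section 11.2 allows 'Related' only when no other cause is reasonable, which conflicts with the 'reasonable possibility' threshold in 11.1 and 11.3 and leaves some two-cause events with no class

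*Combined protocol and SAP*

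**What the plan says.** Section 11.2 (Causality) is mandatory: the relationship of each event to the trial medication "must be determined by a medically qualified individual according to the following definitions". Two classes follow. 'Related' needs a reasonable temporal sequence and adds "It cannot reasonably be attributed to any other cause". 'Not Related' reads "The adverse event is probably produced by the participant's clinical state or by other modes of therapy administered to the participant".

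Section 11.1 (Definitions) sets the threshold for an adverse reaction at a causal relationship that is "at least a reasonable possibility, i.e. the relationship cannot be ruled out". Its row for a serious adverse reaction uses a different wording: "believed with reasonable probability to be due to one of the trial treatments".

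Section 11.3 (Procedures for Recording Adverse Events) takes all events up to 24 hours after the scan. Its rule for later events begins "Thereafter only adverse events where there is a reasonable possibility of a relationship to inhaled xenon", equates these with adverse reactions, and adds events that the chief investigator considers medically important. The same section makes relatedness a recorded item and ties a follow-up rule to it: "AEs considered related to inhaled xenon as judged by a medically qualified investigator or the Sponsor will be followed either until resolution", or until the event is considered stable.

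**The concern.** The protocol uses one idea, relatedness to xenon, with different thresholds in adjacent sections. Section 11.1 asks whether xenon can be ruled out. Section 11.2 asks whether everything else can be ruled out. These are close to opposite tests, and they disagree whenever two causes are both reasonable.

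Such events are foreseeable here. Every participant is a candidate for radiotherapy, some with chemotherapy, and patients with lung cancer are also offered a gadolinium agent in the same imaging session as xenon. At stake is the relatedness tabulation for an investigational gas. If 11.2 is applied as written, that tabulation will not match the protocol's own definition of an adverse reaction, and some events may have no valid entry.

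**Working it through.** No figure in the plan bears on this and no arithmetic decides it. The check is to apply each section's wording to the same events.

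**Step 1: the tests side by side.**
- 11.1, adverse reaction: xenon is a reasonable possibility. Other causes do not matter.
- 11.1, serious adverse reaction: reasonable probability, on its face a stronger word than possibility.
- 11.2, 'Related': plausible timing, and no other reasonable cause.
- 11.2, 'Not Related': the participant's condition or another therapy is the probable cause.
- 11.3, recording after 24 hours: reasonable possibility, as in 11.1.

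**Step 2: apply them.** Take events with plausible timing for which xenon is a reasonable possibility.

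| Other cause | 11.1 | 11.2 |
|---|---|---|
| None reasonable | Adverse reaction | Related |
| Reasonable, not probable | Adverse reaction | Neither class |
| Probable, but xenon not ruled out | Adverse reaction | Not Related, if that cause is the clinical state or another therapy |

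The sections agree only in the first row.

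**Step 3: direction.** An event that meets 11.2 'Related' has plausible timing and no other reasonable cause, so it also meets 11.1. The reverse fails in rows two and three. Relative to 11.1, section 11.2 can therefore only take events out of 'Related'. Where they land is not fixed, because no default class is given.

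**Step 4: can rows two and three occur?** Section 10.1 (Side effects) lists headache (0.4%) and nausea or vomiting (0.2%) for xenon. Section 9.5 (Safety considerations for MultiHance) lists headache and nausea as common for the gadolinium agent, between 1/100 and 1/10, and the preceding description allows that scan straight after the xenon scan. The overlap is in the document itself. The xenon percentages come from 4 minutes 20 seconds of continuous breathing, which 10.1 contrasts with this trial's single breath, so they show that symptoms overlap and do not give a rate. Section 10.1 also reports mild gastrointestinal symptoms in 32% of 44 volunteers, in a study it groups with single breath-hold experiments, without saying that these were nausea. Overlap with symptoms of radiotherapy or chemotherapy is plausible but is my inference.

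**Step 5: opportunity.** Under 7.1, gadolinium is offered with xenon at Visits 2, 4 and 5, so at 3 of the 4 planned imaging visits for a patient with lung cancer, and at none for other diagnoses. With 30 patients all having lung cancer, that is 30 × 3 = 90 of 30 × 4 = 120 planned sessions. The number with lung cancer is not stated, so the planned count lies between 0 and 90. These are planned-visit counts for 30 patients and not upper limits: 12.4 speaks of at least 30 patients, and 9.5 lets a patient return to complete a visit's imaging. They are not counts of misclassified events.

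**The case against.** The strongest case on the other side is that the protocol already applies the broad threshold where it matters most. Section 11.1 counts as an adverse reaction any case in which either the reporting professional or the Sponsor reasonably suspects a causal link, and 11.3 uses that threshold for late recording. The follow-up rule can be triggered by the Sponsor as well as by the investigator. Section 11.3 also provides care whatever the cause: "In the event of symptoms arising, patients will be given appropriate care and medical supervision until symptoms resolve, or the condition becomes stable". Section 9.10 adds follow-up for anyone withdrawn because of an adverse event. SAEs go to R&D and are reviewed under 11.4 and 11.7 without a relatedness condition. Relatedness is not an endpoint, and there is no randomised comparison to bias. The usual xenon effects resolve within 2–3 minutes, so most would still be 'Related'.

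All of this stands, and it limits the consequence. It does not remove the conflict: nothing links the broad threshold to the mandatory 11.2 assessment that produces the CRF entry.

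A reader might go further in three ways, and the documents support none of them.
- That every disputed event ends as 'Not Related'. That class needs a probable cause in the patient's condition or another therapy. A gadolinium imaging agent is arguably neither, so an event may be left with no class.
- That reportable reactions would be missed. Adverse reactions, serious adverse reactions and SUSARs have their own definitions, and are affected by 11.2 only if assessors carry its judgement across.
- That a number of misclassified events can be given. Multiplying sessions by the gadolinium side-effect band would count gadolinium effects, not events for which xenon is also a reasonable cause.

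**Conclusion.** The point holds as an internal contradiction in current text. An event with two reasonable causes is an adverse reaction under 11.1 but outside 'Related' under 11.2, and the two 11.2 classes are not exhaustive. The 'reasonable probability' wording in the serious adverse reaction row is a further unreconciled threshold.

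The size is modest: one CRF item and one follow-up rule, the latter with the Sponsor's judgement as a second trigger. The frequency is unknown and cannot be derived from the document. The conclusion assumes that the two sentences under 'Related' are joint conditions, which is their natural reading, and that assessors apply 11.2 literally, as it instructs. It depends on none of the counts above. The text should be corrected, but the point does not call into question the protocol's capture of adverse events to 24 hours or its handling of SAEs.

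**What to change.** Reword 11.2 to the threshold already in 11.1, with two classes that cover every event:
- Related: a causal relationship with xenon is at least a reasonable possibility, even if another cause is also possible.
- Not related: there is no reasonable possibility of a causal relationship with xenon.

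Align the serious adverse reaction row in 11.1 with the adverse reaction definition, for example as a serious adverse event that meets that definition. Leave the 11.3 threshold as it is.

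Before the final report, re-check all recorded events classed 'Not Related' or left unclassified. Use existing CRF data: description, timing, whether gadolinium was given that day, and the entry for another suspect drug or device. That entry alone is not enough, because it need not record underlying disease or radiotherapy.

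The cost is one paragraph and one table row in an amendment, with Sponsor approval before submission (section 21) and the approvals in 16.3 if the amendment is substantial, plus a desk review in a trial planned for 30 patients. The downside is slightly more events classed as reactions.

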### **11.3. Procedures for Recording Adverse Events**

All AEs observed by the investigator or reported by the patient during and for 24 hours after Xe-129 lung MRI are reported on the case report forms. A member of the research team will contact the participant by telephone 24 hours after completion of hyperpolarized Xe-129 MR imaging to record any AEs that may have occurred after leaving the hospital. These will be clearly documented on the patient CRFs. Thereafter only adverse events where there is a reasonable possibility of a relationship to inhaled xenon (adverse reactions) as judged by the chief investigator, and any adverse event considered by the chief investigator to be of medical interest/importance are reported. These events will be reported on the case report forms.

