**Computed Tomography (CT)**

Thoracic CT will be performed at the Churchill Hospital. An injection of iodinated contrast will be administered through the same cannula that was inserted for the nuclear medicine scan. Scanning takes place 50-60 seconds post injection as per standard imaging protocol. CT images will be acquired during a single breath hold performed triggered to lung volume. The patient lies on their back, whilst scanning takes place.

Participants will be screened for contraindications to iodinated contrast prior to completion of this study measure. These include: -

- Marked renal failure not on dialysis
- Known allergy to contrast medium, history of anaphylaxis
- Known or suspected thyroid carcinoma
- Inability to gain intra-venous access

If contraindication to iodinated contrast is identified, all thoracic CT scans will be performed without contrast. This will not exclude the patient from participating in the study.

Software will be used to determine areas of lung attenuation, such as delineating areas < -950 HU validated by visual inspection by an experienced thoracic radiologists, and/ or other measures of local texture in CT imaging. Comparisons with manual region of interest performed on an image display software (OsiriX) will be made.

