**11.4. Reporting Procedures for Serious Adverse Events**

All SAEs (other than those defined in the protocol as not requiring reporting) following Xe-129 lung MRI scanning must be reported on the SAE reporting form to R&D within 24 hours of the Site Study Team becoming aware of the event. R&D will perform an initial check of the report, request any additional information, and ensure it is reviewed by the Medical Monitor on a weekly basis. It will also be reviewed at the next Trial Safety Group meeting. All SAE information must be recorded on an SAE form and faxed, or scanned and emailed, to R&D. Additional and further requested information (follow-up or corrections to the original case) will be detailed on a new SAE Report Form and faxed/mailed to R&D.

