**16.7. Other Ethical Considerations**

This type of imaging research raises several ethical issues. The proposed hyperpolarized Xe-129 MR, gadolinium-enhanced lung MRI and optional ventilation/perfusion nuclear medicine scan will be provided in addition to any routine scans. Additional imaging may or may not add any information that will benefit the individual patient. Nuclear medicine and CT examinations involve ionizing radiation and there is a small but quantifiable risk associated with administration of iodinated contrast. These issues will be addressed as follows:

- Baseline and follow-up CT scans form part of standard routine patient care. Nuclear medicine scans are considered negligible exposure in comparison to doses from radiotherapy itself. However, any additional exposure will be formally justified.

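### Mandatory AE and SAE recording opens with the Xe-129 MRI, so an acute reaction to the research-only V/Q scan before it has no mandatory route, and relatedness is assessed only against xenon

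*Combined protocol and SAP*

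**What the plan says.** **Recording window.** Section 11.3 has all adverse events observed by the investigator or "reported by the patient during and for 24 hours after Xe-129 lung MRI are reported on the case report forms". After that, the mandatory part covers events with a reasonable possibility of a link to inhaled xenon. Beyond those, "any adverse event considered by the chief investigator to be of medical interest/importance are reported".

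**Serious events.** Section 11.4 says that SAEs "following Xe-129 lung MRI scanning must be reported on the SAE reporting form to R&D within 24 hours" of the site team becoming aware. It sets no end date and no relatedness condition, but the trigger is again the xenon scan.

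**Causality.** Section 11.2: "The relationship of each adverse event to the trial medication must be determined by a medically qualified individual". The trial medication is xenon (Synopsis; section 10.1). There are two categories, Related and Not Related. Section 11.3 also has each recorded event carry an entry for any other suspect drug or device.

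**Study-only procedures.** Section 16.7 says that, besides the xenon MRI, "gadolinium-enhanced lung MRI and optional ventilation/perfusion nuclear medicine scan will be provided in addition to any routine scans". It treats thoracic CT as routine care. V/Q is offered at baseline only, and sections 9.6 and 9.9 list neither V/Q nor gadolinium for participants without lung cancer.

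**Order of scans.** The CT part of section 9.5 states: "An injection of iodinated contrast will be administered through the same cannula that was inserted for the nuclear medicine scan". The gadolinium part of the same section says that this cannula, already used for nuclear medicine and CT, is used again, and that the patient stays on the bed after the xenon MRI.

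**The concern.** Participants have the V/Q scan, and the cannula placed for it, only because they joined the trial. The protocol foresees a hazard: section 9.5 screens for known hypersensitivity to albumin. Yet the obligation to record adverse events begins with a later procedure. A reaction to the tracer or the cannulation that occurs and settles before xenon need not be entered as an AE, and a serious one need not be sent to R&D. The Trials Safety Group (section 11.7) reviews reported SAEs, so it need not see such an event.

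The second element concerns classification. Gadolinium events are collected when they occur soon after the scan. The only formal relatedness judgement on them, however, is whether xenon was the cause. The trial would have no defined assessment of whether its other research procedures caused harm.

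**Working it through.** No sample size, power or error-rate figure in the plan bears on this, so there is none to reproduce. The check is of text, followed by arithmetic on gadolinium exposure.

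**Step 1: order of procedures.** The flow charts are not available in the text, so the order is inferred.

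- The cannula is placed for V/Q and reused for CT (section 9.5, CT). Hence V/Q precedes CT.
- The same cannula, already used for both, serves gadolinium (section 9.5, gadolinium). Hence V/Q and CT precede gadolinium.
- Gadolinium is given straight after the xenon MRI on the same bed (section 9.5, gadolinium and MultiHance). Hence V/Q does not fit between xenon and gadolinium, and falls before xenon.

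Section 7.1 names the xenon MRI before V/Q, but in a list of what is offered, not as a sequence.

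**Step 2: apply the rules to each case.**

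| Event | 11.3 (AE) | 11.4 (SAE) | Other text |
|---|---|---|---|
| V/Q or cannulation reaction, over before xenon, participant continues | Window not yet open | Not after a xenon scan | Later visits ask about any AE (9.8), but recording a non-xenon event then rests on chief investigator discretion (11.3) |
| Same reaction, still present at xenon or arising within 24 hours after it | Recorded | Reported if serious | None needed |
| Reaction that leads to withdrawal before xenon | Window never opens | Trigger never met | 9.10: reason entered in the CRF, event followed until resolved or stable |
| Gadolinium event within 24 hours of the xenon MRI | Recorded | Reported if serious | Gadolinium can be entered as another suspect drug |
| Non-serious gadolinium event after 24 hours | Only if possibly xenon-related or judged of interest | Not applicable | Later-visit enquiry (9.8) |

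The first row has no mandatory route. The third has a CRF entry and follow-up, but no AE or SAE report.

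**Step 3: causality.** Related requires, among other things, that "It cannot reasonably be attributed to any other cause". Gadolinium given straight after xenon supplies another reasonable cause, so a reaction to it is unlikely to meet that test. Not Related refers to the clinical state or to events probably produced "by other modes of therapy administered to the participant". A diagnostic contrast agent is not plainly a therapy. Neither category assesses gadolinium or V/Q.

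**Step 4: gadolinium exposure.** Inputs: 30 participants (section 12.2); gadolinium at Visits 2, 4 and 5 for lung cancer participants (sections 7.1 and 9.8); MultiHance rates from section 9.5, 0.01 to 0.10 for common effects and 0.0001 to 0.001 for rare allergic or other serious effects. The number with lung cancer is not stated. I assume 10 to 30, with 1 to 3 injections each, because the one compulsory follow-up may be the half-way visit, which has no gadolinium.

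- Upper bound on injections: 30 × 3 = 90. Lower end of the assumed range: 10 × 1 = 10.
- Expected number of each common effect at the upper bound: 90 × 0.01 = 0.9 to 90 × 0.10 = 9.
- Chance of at least one, treating injections as independent: 1 − (1 − p)^N.
  - Common effect: 1 − 0.99^10 = 9.6%, up to 1 − 0.90^90 > 99.9%.
  - Rare effect: 1 − 0.9999^10 = 0.1%, up to 1 − 0.999^90 = 8.6%.

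These figures describe events lacking a relatedness assessment of their own, not events lost. For V/Q there are at most 30 scans, and the documents give no event rate.

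**The case against.** The case against is strong on several points, and most of it stands.

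- A reader might infer that nothing is recorded if a V/Q reaction keeps a participant from xenon. Section 9.10 contradicts this: the reason for withdrawal goes in the CRF and the event is followed. It does not, however, create an AE or SAE report, and it does not cover participants who continue.
- A reader might infer that gadolinium harms escape the Trials Safety Group. They do not: 11.3 takes all events within 24 hours whatever their cause, and 11.4 takes SAEs after the xenon MRI.
- A reader might infer that the plan classes gadolinium reactions as Not Related. No text says so. That entry would be correct with respect to xenon, and the other-suspect-drug item already lets gadolinium be named. What remains is that naming a suspect agent is not a defined relatedness judgement.
- A recording window narrower than the AE definition in 11.1 is not a contradiction, since a definition and a recording rule do different work.
- The plan contains no comparison of AE rates between diagnosis groups, so an argument that such rates mix exposures has no target.
- The scan order is inferred. If V/Q and xenon share a visit, as cannula reuse suggests, a reaction persisting into the xenon session is recorded. The gap is then limited to reactions that end, or stop the participant, before xenon.

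**Conclusion.** The point holds in a limited form and is worth correcting because the remedy is cheap. An acute V/Q or cannulation reaction before the xenon scan has no mandatory AE or SAE route. Section 9.10 covers only events that lead to withdrawal, and what later-visit enquiry finds is recorded at the chief investigator's discretion unless xenon is suspected. Gadolinium events within 24 hours are recorded and gadolinium SAEs are reported, but no relatedness assessment is defined for any study procedure other than xenon.

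The gap in capture cannot be put as a number, and it affects only lung cancer participants who accept an optional, one-off scan. It would be wrong to take the 0.9 to 9 gadolinium events as its size: early gadolinium events fall inside the recording window, and 90 injections assumes that all 30 participants have lung cancer and attend every visit. The conclusion rests on the scan order read from section 9.5, which the study team can confirm from the flow charts.

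**What to change.** - **11.3:** start mandatory AE recording at the first study-only procedure of a visit (V/Q including its cannulation, xenon including the calibration breath, or gadolinium) and run it to 24 hours after the last one. Extend the rule for later events to those possibly related to any study-only procedure.
- **11.4:** move the start of SAE reporting to the same point. Because 11.4 now has no end date, the 24-hour limit should not be carried into it.
- **11.2 and the forms:** add an assessment of relatedness to a study procedure (V/Q, gadolinium, cannulation) beside relatedness to xenon.

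The cost is protocol wording, one extra field on the AE and SAE forms, and a few more minor events to record. The existing 24-hour call serves when the procedures share a day. If V/Q is done on a separate day, or xenon is never given, one further call is needed. No scan, visit or treatment changes.
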